7.2. Safety Assessments

The use of SinuSonic device is not associated with significant safety concerns in prior studies. However, to assess safety information, study team will conduct a detailed medical review of systems at each visit (including baseline) to establish the presence of any ongoing medical issues at the time of study entry and track changes in these issues during the course of study participation. The medical review of system will

also allow for detection of any new onset medical issue (that may post safety concern) with the use of SinuSonic device. Planned timepoints for all safety assessments are provided in the SoA.

7.2.1. Physical Examinations

- Patients will be evaluated in ENT clinic with nasal endoscopy and/or CT imaging prior to study enrollment as part of standard of care evaluation. If patient has complaint of sinus headache and is without objective evidence of sinonasal inflammation (Lund MacKay score ≤ 3 without a single sinus score of 2), they will be offered referral to the study.
- Investigators should pay special attention to clinical signs related to previous serious illnesses.

7.2.2. Pregnancy Testing

The use of SinuSonic device is not expected to impact fetus. Therefore, pregnancy testing will not be conducted during the course of study. However, if a participant reports becoming pregnant, it will be recorded in the study and outcome of the pregnancy will be monitored with participant's permission.

7.2.3. Suicidal Ideation and Behavior Risk Monitoring

There will not be a separate suicidal ideation and behavior (SIB) risk monitoring as the study device (SinuSonic) is not known to be active in the CNS, will not be studied for activity in CNS, and is not being developed for any psychiatric or neurologic indication. The Sinusonic device is not known to affect mood, cognition, or behavior via their direct or indirect effects on the CNS and the study device is not similar to any other intervention that have had SIB reported. However, information about SIB will be collected as part of the assessment of psychiatric system in the medical review of system.

7.3. Adverse Events (AEs) Serious Adverse Events (SAEs), and Other Safety Reporting

The definitions of device-related safety events, adverse device effects (ADEs), and serious adverse device effects (SADEs) can be found in Appendix 1. Device deficiencies are covered in Section 8.4.9.

The investigator and any qualified designees are responsible for detecting, documenting, and recording events that meet the definition of an AE or SAE and remain responsible for following up AEs that are serious, considered related to the study intervention or study procedures, or that caused the participant to discontinue the study intervention (see Section 7). This includes events reported by the participant (or, when appropriate, by a caregiver, surrogate, or the participant's legally authorized representative).

The method of recording, evaluating, and assessing causality of AEs and SAEs and the procedures for completing and transmitting SAE reports are provided in Appendix 1.

7.3.1. Time Period and Frequency for Collecting AE and SAE Information

All SAEs will be collected from the start of study intervention until exit from the study at the timepoints specified in the SoA (Section 1.3).

All AEs will be collected from the start of study intervention until the exit from study at the timepoints specified in the SoA (Section 1.3).

Medical occurrences that begin before the start of study intervention but after obtaining informed consent will be recorded as medical history/current medical conditions, not as AEs.

All SAEs will be recorded and reported to the sponsor or designee immediately and under no circumstance should this exceed 24 hours, as indicated in Appendix 1. The investigator will submit any updated SAE data to the sponsor within 24 hours of it being available.

Investigators are not obligated to actively seek information on AEs or SAEs after conclusion of the study participation. However, if the investigator learns of any SAE, including a death, at any time after a participant has been discharged from the study, and the investigator considers the event to be reasonably related to the study intervention or study participation, the investigator must promptly notify the sponsor.

7.3.2. Method of Detecting AEs and SAEs

Care will be taken not to introduce bias when detecting AEs and/or SAEs. Open-ended and nonleading verbal questioning of the participant is the preferred method to inquire about AE occurrences.

7.3.3. Follow-up of AEs and SAEs

After the initial AE/SAE report, the investigator is required to proactively follow each participant at subsequent visits/contacts. All SAEs will be followed until resolution, stabilization, the event is otherwise explained, or the participant is lost to follow-up (as defined in Section 7.3). Further information on follow-up procedures is provided in Appendix 1.

7.3.4. Regulatory Reporting Requirements for SAEs

- Prompt notification by the investigator to the sponsor of an SAE is essential so that legal obligations and ethical responsibilities towards the safety of participants and the safety of a study intervention under clinical investigation are met.
- The sponsor has a legal responsibility to notify both the local regulatory authority and other regulatory agencies about the safety of a study intervention under clinical investigation. The sponsor will comply with country-specific regulatory requirements relating to safety reporting to the regulatory authority, institutional review boards (IRBs)/independent ethics committees (IECs), and investigators.
- An investigator who receives an investigator safety report describing an SAE or other specific safety information (e.g., summary or listing of SAEs) from the sponsor will review and then file it along with the IDFU and will notify the IRB/IEC, if appropriate according to local requirements.

7.3.5. Disease-related Events and/or Disease-related Outcomes Not Qualifying as AEs or SAEs

The following disease-related events (DREs) are common in participants with Sinus Headache and can be serious/life threatening:

- None

Because these events are typically associated with the disease under study, they will not be reported according to the standard process for expedited reporting of SAEs even though the event may meet the definition of an SAE. These events will be recorded within the appropriate timeframe.

NOTE: However, if either of the following conditions applies, then the event must be recorded and reported as an AE/SAE (instead of a DRE):

The event is, in the investigator's opinion, of greater intensity, frequency, or duration than expected for the individual participant.

The investigator considers that there is a reasonable possibility that the event was related to study intervention.

7.3.6. Medical Device Deficiencies

Medical devices are being provided for use in this study as the study intervention. To fulfill regulatory reporting obligations worldwide, the investigator is responsible for the detection and documentation of events meeting the definitions of device deficiency that occur during the study with such devices.

The definition of a medical device deficiency can be found in Appendix 1.

NOTE: Deficiencies fulfilling the definition of an AE/SAE will follow the processes outlined in Appendix 1 of the protocol.

7.3.6.1. Time Period for Detecting Medical Device Deficiencies

- Medical device deficiencies that result in an incident will be detected, documented, and reported during all periods of the study in which the medical device is used.
- If the investigator learns of any device deficiency at any time after a participant has been discharged from the study, and such a deficiency is considered reasonably related to a medical device provided for the study, the investigator will promptly notify the sponsor.

The method of documenting medical device deficiencies is provided in Appendix 1.

7.3.6.2. Follow-up of Medical Device Deficiencies

- Follow-up applies to all participants, including those who discontinue study intervention.
- The investigator is responsible for ensuring that follow-up includes any supplemental investigations as indicated to elucidate the nature and/or causality of the deficiency.
- New or updated information will be recorded on the originally completed form with all changes signed and dated by the investigator.

7.3.6.3. Prompt Reporting of Device Deficiencies to the Sponsor

- Device deficiencies will be reported to the sponsor within 24 hours after the investigator determines that the event meets the protocol definition of a medical device deficiency.
- The medical device deficiency report form will be sent to the sponsor by email.
- The sponsor will be the contact for the receipt of device deficiency reports.

7.3.6.4. Regulatory Reporting Requirements for Device Deficiencies

- The investigator will promptly report all device deficiencies occurring with any medical device provided for use in the study in order for the sponsor to fulfill the legal responsibility to notify appropriate regulatory authorities and other entities about certain safety information relating to medical devices being used in clinical studies.
- The investigator, or responsible person according to local requirements (eg, the head of the medical institution), will comply with the applicable local regulatory requirements relating to the reporting of device deficiencies to the IRB/IEC.

8. Statistical Considerations

The analysis and reporting will be done on all data from all participants at the time the study ends.

8.1. Statistical Hypotheses

The primary objective is to demonstrate that Sinusonic device is superior to Sham control in achieving improvements in facial pain measured by facial pain VAS, and BPI-SF at 8 weeks. Thus, the null hypothesis to be tested in relation to the primary estimand is as follows:

- Null hypothesis: Sinusonic is not different from sham control with respect to the achievement of improvement in facial pain VAS, and BPI-SF at 8 weeks.

The null and alternative hypotheses corresponding to the secondary estimands are as follows:

Secondary objective [1]:

- Null hypothesis: SinuSonic device is not different from Sham control with respect to the achievement of adverse event rate at 8 weeks.

Secondary objective [2]:

- Null hypothesis: Sinusonic device is not different from Sham control with respect to device satisfaction rate at 8 weeks

8.1.1. Multiplicity Adjustment

A closed testing procedure that controls the family wise error rate in the strong sense at the overall [5]% level will be applied. The statistical comparisons for the primary efficacy endpoint and the key secondary endpoints will be carried out in the hierarchical order as indicated in Section 9.1. This means that the statistical hypotheses are tested in the prespecified order at the same significance level of $\alpha = [0.05]$ as long as all preceding hypotheses are rejected. Once a hypothesis is not rejected, subsequent hypotheses cannot be formally tested and therefore cannot be rejected.

8.2. Analysis Sets

Example 1:

For the purposes of analysis, the following analysis sets are defined:

Participant Analysis Set	Description
Full analysis set (FAS)	
 • All randomized participants.
Safety analysis set (SAS)	
 • All participants who are exposed to investigational intervention.

The full analysis set will be used to analyze endpoints related to the efficacy objectives and the safety analysis set will be used to analyze the endpoints and assessments related to safety.

For the efficacy analyses, participants will be included in the analyses according to the planned investigational intervention; whereas for safety analyses, participants will be included in the analyses according to the investigational intervention they received.

8.3. Statistical Analyses

8.3.1. General Considerations

Statistical analysis will be conducted using SPSS version 25 (Armonk, NY: IBM Corp). Descriptive statistics such as means, range, standard deviations, frequencies, and percentages will be generated in order to present the baseline characteristics of both treatment arms. All continuous variables will be tested for normal distribution as determined by the Shapiro-Wilk test. To evaluate differences in outcome metrics between treatment arms (SinuSonic group vs sham control), paired t-tests will be used for normally distributed variables. Wilcoxon signed rank tests were used for non-normally distributed or ordinal variables. For all tests, a value of $p \leq 0.05$ will be considered statistically significant. The mean change between baseline and follow-up variables of interest will be calculated and measured against previously reported MCID thresholds when available or by using one-half of the baseline SD if not previously reported. Any missing data points will be excluded from analysis and handled similarly across all data points.

8.3.1.1. Main Analytical Approach

Statistical analysis will be conducted using SPSS version 25 (Armonk, NY: IBM Corp). Descriptive statistics such as means, range, standard deviations, frequencies, and percentages will be generated in order to present the baseline characteristics of both treatment arms. All continuous variables will be tested for normal distribution as determined by the Shapiro-Wilk test. To evaluate differences in outcome metrics between treatment arms (SinuSonic group vs sham control), paired t-tests will be used for normally distributed variables. Wilcoxon signed rank tests were used for non-normally distributed or ordinal variables. For all tests, a value of $p \leq 0.05$ will be considered statistically significant. The mean change between baseline and follow-up variables of interest will be calculated and measured against previously reported MCID thresholds when available or by using one-half of the baseline SD if not previously reported. Any missing data points will be excluded from analysis and handled similarly across all data points.

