2.3.3. Overall Benefit Risk Conclusion

Taking into account the measures taken to minimize risk to participants participating in this study, the potential risks identified in association with the SinuSonic device are justified by the anticipated benefits that may be afforded to participants with Sinus headache.

3. Objectives, Endpoints, and Estimands

Objectives	Endpoints
Primary	

 To determine superiority of SinuSonic intervention versus control in treatment of facial pain for patients with complaint of sinus headache that lack objective evidence of sinonasal inflammation 	
 Change in facial pain visual analogue scale at 8 weeks Change in Brief Pain Inventory Short Form at 8 weeks
Secondary	

 To determine safety of device use 	
 Number and percent of subjects reporting pain with device use Number and percent of subjects reporting epistaxis Change in Nasal Obstruction Symptom Evaluation (NOSE) Score at 8 weeks
Tertiary	

 To determine device use satisfaction 	
 Number and percent of subjects that would use the device again Number and percent of subjects that would recommend the device to others

Primary estimand

The primary clinical question of interest is:

What is the improvement in facial pain measured by facial pain VAS, and BPI-SF in patients with sinus headache treated with SinuSonic device versus a sham device regardless of discontinuation of investigational intervention for any reason and regardless of initiation of rescue medication or change in background medication.

The estimand is described by the following attributes:

- Population: Patients with complaint of sinus headache lacking objective evidence of sinonasal inflammation of nasal endoscopy or imaging
- Endpoint: change from baseline to 8 weeks in facial pain VAS, and BPI-SF
- Treatment condition:

the investigational interventions regardless of discontinuation for any reason, with or without rescue medication or change in background medication (treatment policy strategy).

- Remaining intercurrent events:

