The intercurrent events “intervention discontinuation for any reason” and “initiation of rescue medication or change in background medication (dose and product)” are addressed by the treatment condition of interest attribute. There are no remaining intercurrent events anticipated at this time.

- Population-level summary:

difference in mean changes between treatment conditions

Rationale for estimand: Facial pain is the primary complaint impacting quality-of-life in patients with sinus headache. Thus, we propose using 3 validated pain metrics to assess response to therapy. , .

Secondary estimand(s)

The clinical question of interest is for the secondary objective :

What is the difference in the proportion of sinus headache patients experiencing adverse events of pain and epistaxis between investigational SinuSonic treatment arm compared to sham control arm.

The estimand is described by the following attributes:

- Population:

Patients with Sinus Headache

- Endpoint:

Number and percent of subjects reporting pain with device use. Number and percent of subjects reporting epistaxis.

Nasal obstruction symptom evaluation (NOSE) Score change

- Treatment condition:

the investigational interventions regardless of discontinuation for any reason, with or without rescue medication or change in background medication (treatment policy strategy)

- Remaining intercurrent events:

- The intercurrent events “intervention discontinuation for any reason” and “initiation of rescue medication or change in background medication (dose and product)” are addressed by the treatment condition of interest attribute. There are no remaining intercurrent events anticipated at this time

- Population-level summary:

Difference in proportion of patients experiencing adverse event

Rationale for estimand: Safety is a secondary endpoint and will be assessed by specifically tracking incidence of pain with device use and epistaxis. These adverse events are based on prior study results.

4. Study Design

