7.1. Efficacy and/or Immunogenicity Assessments

Study outcomes will be assessed using the facial pain visual analogue scale (VAS)⁵, and Brief Pain Inventory-Short Form (BPI-SF)^{13,14}. The facial pain VAS score is a scale from 0-100 millimeters (mm) and asks patients to rate the severity of their facial pain over a previous one week recall period with higher scores indicating greater pain intensity. Additionally, a current VAS pain score and an immediate 5-minute post-use current VAS pain score will be assessed. A prior study looking at orofacial pain reported a minimal clinically important difference (MCID) of 1.2 for VAS pain. The BPI-SF assesses pain at its “worst”, “least”, “mean”, and “now” (current pain). In clinical trials, the items “worst” and “mean” have been each used singly to represent the pain severity. Worst and mean pain will be assessed over a previous one week recall period. BPI-SF also measures how much pain interferes (BPI interference) with seven daily activities including general activity, walking, work, mood, enjoyment of life, relations with others, and sleep. BPI pain interference is typically scored as the mean of the seven interference items. All items are rated on a 0-10 scale with 0 representing no pain/no interference and 10 representing pain as bad as you can imagine/interferes completely. A distribution-based approach using one-half the SD will be used to determine MCID values for BPI-SF, as there is a paucity of research assessing the MCIDs for these pain measures for facial pain/headache. Planned timepoints for all efficacy assessments are provided in the SoA.

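### The normality pre-test leaves the primary test unfixed, and its rank-test branch does not match the plan's own difference in mean changes

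*Combined protocol and SAP*

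**What the plan says.** Sections 8.3.1 and 8.3.1.1 carry identical text, and it is the only rule for the main comparison of SinuSonic with sham. The first step is a distribution check: "All continuous variables will be tested for normal distribution as determined by the Shapiro-Wilk test". The second step depends on the result: "paired t-tests will be used for normally distributed variables", and then "Wilcoxon signed rank tests were used for non-normally distributed or ordinal variables".

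The primary estimand in Section 3 is specific. It reads "Endpoint: change from baseline to 8 weeks in facial pain VAS, and BPI-SF", and its population-level summary is the "difference in mean changes between treatment conditions".

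On the measures, Section 7.1 describes the VAS as 0-100 mm (Table 1 of the synopsis has 0-10) and says of the BPI-SF, "All items are rated on a 0-10 scale". Neither is classed as continuous or ordinal.

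For the main analysis, Section 8.3.1.1 promises mean change set against MCID thresholds. It promises no between-arm mean difference with a confidence interval. Section 8.3.2 promises arm differences with 95% CIs, but for subgroups, and defers further detail to a SAP. No separate SAP text is in the document.

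**The concern.** A reader of Section 8.3.1.1 cannot say which test will decide the trial. That depends on a check with no stated level, applied to data that are not named: baseline, Week 8 or change scores, pooled or by arm. It also depends on whether a 0-10 rating is held to be ordinal, which the plan leaves open.

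The two branches also answer different questions. A t-type comparison addresses a difference in means. A rank comparison of two independent groups addresses whether values in one group tend to exceed those in the other. If the rank branch is taken, the plan's own summary is neither tested nor estimated. Section 8.1 names both VAS and BPI-SF in the primary hypothesis, so one could be judged on means and the other on ranks.

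**Working it through.** **The plan's own figure.** Section 8.4 claims over 90% power for 30% vs 70% responders, N = 60 randomised 1:1 (30 per arm), two-sided 5%.
- Unpooled: SE = sqrt(2 × 0.3 × 0.7 / 30) = 0.1183; 0.4 / 0.1183 − 1.96 = 1.42; power 92.2%.
- Pooled null variance: SE0 = sqrt(2 × 0.25 / 30) = 0.1291; (0.4 − 1.96 × 0.1291) / 0.1183 = 1.24; power 89.3%.

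The claim is reproduced by the unpooled form. It concerns responder proportions, which neither branch of Section 8.3.1.1 tests. It does show that the plan expects a mix of responders and non-responders, a shape that a normality check may reject.

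**Simulation of the two-step rule.** From the documents: 30 per arm, alpha 0.05, VAS bounded at 0-100 mm, entry VAS ≥5 on 0-10 (50 mm), pilot VAS 59.6 (SD 15.7) falling to 34.6 (SD 21.7). Assumed: Shapiro-Wilk at 0.05 on each arm's change scores; t-test if both arms pass, otherwise a rank-sum test. Independent-sample tests are used because the arms are independent. Runs are of 3,000 or 4,000 trials; the Monte Carlo standard error at 5% is sqrt(0.05 × 0.95 / 4000) = 0.34 points.

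In the responder mixtures, non-responders drop 2 (SD 12) mm. Sham has 30% responders and active has 30%, 55% or 70%. In the 40 mm case the responder drop has SD 15 mm.

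| Assumed change scores | Test switched | Switched and t-test and rank test disagree |
|---|---|---|
| Exactly normal | about 10% | not tallied |
| Bounded VAS from pilot SDs | 7-10% | not tallied |
| Mixture, responder drop 25 mm | 21-30% | 0.8-2.0% (25 and 30 mm together) |
| Mixture, responder drop 30 mm | 25-40% | as above |
| Mixture, responder drop 40 mm | 56-71% over repeated runs | 1.5-3.8% |

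The normal row agrees with arithmetic: two checks at 5% give 1 − 0.95² = 9.75%. Chance alone would move about one trial in ten to the rank branch.

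**Type I error, identical arms.** Two-step rule against t-test: 5.4% vs 5.4%, 5.9% vs 5.8%, 5.3% vs 5.1%. With a real effect, one example gives 74.7% vs 75.5% power.

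**Equal means, different shapes.** Let sham change be normal (mean 0, SD 1). Let active be 30% at −2.1 and 70% at +0.9, each with SD 0.7.
- Active mean: 0.3 × (−2.1) + 0.7 × 0.9 = 0, so the plan's estimand is zero.
- Rank-test target, the probability that an active change exceeds a sham change: the SD of a difference is sqrt(0.49 + 1) = 1.221, so 0.7 × Φ(0.9/1.221) + 0.3 × Φ(−2.1/1.221) = 0.7 × 0.770 + 0.3 × 0.043 = 0.55, not 0.50.

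Here the test is switched in 85% of trials, and the two-step rule rejects in 11.2% against 5.6% for the t-test. Similar settings on the mm scale gave 12.6% vs 5.1% and 14.6% vs 5.6%. With a wider sham spread the excess nearly vanished: 6.0% vs 5.6% and 7.1% vs 5.7%.

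**The case against.** **The numerical effect is small.** This stands. Counting every trial where the two tests disagree gives roughly 2% to 5%, but that includes trials that never switch. The relevant figure is about 1% to 4%. A reader might infer that the pre-test inflates the false-positive rate. With identical arms it does not.

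**The high switching rates rest on an assumed scenario.** This also stands. A reader might take a rate near 60-70% as the expected one. It needs responder drops of 40 mm against 2 mm, and the documents give no changes by responder status. Settings close to the pilot SDs give 7% to 10%. At the other extreme, exponential changes switch nearly every trial, but nothing in the documents supports that shape.

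**The equal-means example is constructed.** It is, and it depends on the shapes chosen. In that example the 0.55 leans towards worse changes on the active device, so the excess rejections would favour sham. It shows that the rank branch has another target. It does not show that the plan is biased towards the device.

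**The rule is prespecified.** Only partly, since its level, its input data and the class of each measure are missing. A reader might go further and suppose that the data choose the ordinal route, or that an analyst will compare both p-values first. The documents support neither: the ordinal route is a rule by variable type, left open only because the measures are not classed, and no such comparison is described.

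**The more basic fault is that both named tests are for paired data.** That is a separate error in the same sentences. Putting independent-sample versions in their place leaves the pre-test and the mismatch where they are.

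**Mean change is calculated in any case, and a SAP may add detail.** Mean change set against an MCID is not a between-arm difference with an interval. The deferral to a SAP stands in the subgroup section and overrides nothing here.

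**Conclusion.** Wrong as written. The primary test is not fixed in advance, and one of its two branches does not address the estimand in Section 3. The harm is mainly to the estimand and to pre-specification: a result could be reported with no estimate of the quantity that the plan set out to measure.

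The numerical consequence is usually modest: switching in about 7% to 70% of trials, a changed conclusion in about 1% to 4%, and type I error near 5% with identical arms. Rejection above 10% with equal means occurs only for some differences in shape. All of this rests on assumed distributions, a 0.05 level for Shapiro-Wilk, the check being applied to each arm's change scores, and independent-sample tests in place of the paired ones.

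At about 30 per arm on bounded scales, inference on a mean difference does not need normal raw values, so the pre-test buys little.

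**What to change.** In Sections 8.3.1 and 8.3.1.1, delete the pre-test and the branch that follows it. Name one primary analysis for VAS and one for a single named BPI-SF score: a linear model of the Week 8 score on arm and baseline score, reporting the adjusted between-arm mean difference and 95% CI whatever the distribution. With baseline in the model, that difference addresses the difference in mean changes. State which pre-treatment record is the baseline for each measure. Site may be added, as there are three sites, but this is optional. Keep a two-sample rank test only as a named sensitivity analysis.

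An unadjusted two-sample comparison of mean change with a CI would also match the estimand. Baseline adjustment is a free gain in precision, because pre-treatment scores are already collected. The same rewrite removes the paired-test error. The cost is wording only: no added participants, visits or data.

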4.1. Overall Design

- This is a parallel, two-arm, sham placebo controlled multicenter (Mayo AZ, Mayo FL and Mayo RST), clinical trial investigating use of the novel SinuSonic Device for sinus headache.
- The control group will be a sham device of similar appearance to the investigational device
- Participants will be healthy volunteers with complaint of sinus headache lacking objective evidence of sinonasal inflammation on exam or endoscopy
- Primary outcome measures of facial pain measured using facial pain VAS and BPI-SF will be assessed at baseline, Day 1, 2 week, 4 week, 6 week, and 8 weeks.
- Participants will be randomized in a 1:1 fashion; SinuSonic arm: Sham device, respectively.
- Total Duration of study participation will be 11 weeks; 2-3 weeks for screening and randomization and 8 weeks for the intervention component.

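### The SinuSonic-versus-sham comparison is assigned paired tests, but the arms are independent and no valid between-arm test is named for the primary mean change

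*Combined protocol and SAP*

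**What the plan says.** Section 4.1 describes a "parallel, two-arm, sham placebo controlled multicenter" trial with 1:1 randomisation. No matching or crossover appears anywhere in the document.

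Section 3 sets the primary endpoint as "change from baseline to 8 weeks in facial pain VAS, and BPI-SF" and the population-level summary as "difference in mean changes between treatment conditions". The null hypothesis in Section 8.1 is likewise between arms: "Sinusonic is not different from sham control with respect to the achievement of improvement in facial pain VAS", and the same for BPI-SF.

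The analysis text appears twice in the same words, in Sections 8.3.1 and 8.3.1.1: "To evaluate differences in outcome metrics between treatment arms (SinuSonic group vs sham control), paired t-tests will be used for normally distributed variables". The next sentence gives the alternative: "Wilcoxon signed rank tests were used for non-normally distributed or ordinal variables". Mean change is then to be calculated and set against MCID thresholds, with no arm comparison attached to it. On missing values: "Any missing data points will be excluded from analysis and handled similarly across all data points".

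**The concern.** A paired t-test or signed-rank test needs a natural partner for each observation. Two independently randomised arms supply none. The sentence can therefore be read in two ways.

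1. **Literal.** SinuSonic and sham participants are paired in some arbitrary order. The p-value then depends on a pairing that the plan does not define, and observed participants are dropped when the arms end with unequal numbers, although Section 8.2 bases efficacy on all randomised participants.
2. **Within-arm.** Baseline is compared with follow-up inside each arm. That test is valid, but it answers a different question. Placebo response, regression to the mean and natural course are credited to the device, and the null hypothesis in Section 8.1 is never tested.

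These are the only tests named for the primary comparison, so the choice would fall to the analyst after the data exist.

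**Working it through.** **The plan's own figure.** Section 8.4 claims over 90% power for N = 60 with 30% versus 70% responders, two-sided 5%. With 30 per arm:
- Unpooled: 0.40 / sqrt(2 × 0.21/30) − 1.96 = 0.40/0.1183 − 1.96 = 1.42, power 92.2%.
- Pooled: (0.40 − 1.96 × sqrt(2 × 0.25/30)) / 0.1183 = (0.40 − 0.253)/0.1183 = 1.24, power 89.3%.

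The claim reproduces, within rounding, as a comparison of two independent proportions. The sizing thus treats the arms as independent while the analysis text does not, and it concerns responders, not mean change.

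**Inputs for the consequences.** The pilot VAS SDs are 15.7 mm at baseline and 21.7 mm at 4 weeks (Section 2). The documents give neither the SD of change nor the correlation r, so r is assumed:

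SD of change = sqrt(15.7² + 21.7² − 2r × 15.7 × 21.7) = 22.6, 19.4 and 15.5 mm at r = 0.3, 0.5 and 0.7.

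The results below use 30 per arm and r = 0.5 unless stated.

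**Literal reading, one data set re-paired 20,000 times.** At a 10 mm difference, chosen because it is borderline, the independent test gives t = 10 / (19.4 × sqrt(2/30)) = 2.00 on 58 df, p = 0.051.

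| True difference | Paired p, central 95% of pairings | Pairings with p ≤ 0.05 |
|---|---|---|
| 10 mm | 0.019 to 0.098 | about 40% |
| 12 mm | 0.005 to 0.049 | 98% |
| 14 and 16.5 mm | – | 100% |

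**Literal reading, averaged over simulated trials.** Type I error is 5.0%. Paired versus independent power is 49% versus 50% at 10 mm and 89% versus 90% at 16.5 mm, because the degrees of freedom fall from 58 to 29 (critical t from 2.002 to 2.045). The two tests disagree on significance in 1.7% of trials at 0 mm, 6.1% at 10 mm and 2.9% at 16.5 mm.

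**Literal reading, missing data.** The plan gives no dropout rate. With an assumed 10% to 20% missing at week 8, the arms end unequal in 83% to 87% of trials. The loss depends on the pairing rule:
- Paired by row before exclusions, with d the proportion missing: 60(1−d) − 60(1−d)² = 5.4 observed participants lost at 10% and 9.6 at 20%.
- Paired after exclusions: only the arm-size difference is lost, on average 1.8 to 2.5.

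**Within-arm reading, no device effect, assumed improvement shared by both arms.**

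| Shared improvement | Active arm significant, r = 0.5 (r = 0.3; r = 0.7) | Active significant, sham not, r = 0.5 |
|---|---|---|
| 5 mm | 28% (22%; 40%) | 0.28 × 0.72 = 20% |
| 7 mm | 48% (37%; 67%) | 0.48 × 0.52 = 25% |
| 10 mm | 78% (65%; 93%) | 0.78 × 0.22 = 17% |

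A two-sample test would be significant in about 5% of such trials. At a shared 15 mm both arms are significant in 97% of trials (88% at r = 0.3), and at 25 mm in practically all, so the result no longer distinguishes device from sham.

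**The case against.** - **It is a drafting slip that any analyst would correct.** Possibly, but the sentence explicitly attaches paired tests to the arm comparison, appears in two sections and is followed by the matching paired rank test. Nothing elsewhere corrects it.
- **Another section supplies the test.** Section 8.4 uses a two-proportion method for sizing only, and points to a Section 9.3.2 that does not exist. Section 8.3.2 defers further detail to the SAP, but under subgroup analyses. A later document would still have to contradict the section headed as the main analytical approach.
- **The literal reading does little harm on average.** This stands: type I error holds, about 1 point of power is lost, and the wide spread of p-values is confined to borderline results. Participant loss may also be as low as about 2. The objection to this reading is that the p-value is undefined until someone picks a pairing.
- **Not every shared improvement produces significance in the active arm.** This also stands: the improvement must be large enough, and where sham is significant too, a careful reader would not claim superiority. The misleading pattern, active significant and sham not, occurs in 17% to 25% of trials at r = 0.5. That is still well above 5%.

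**Conclusion.** The concern holds and must be fixed. The defect lies in the text and depends on no assumption: the only tests named for the primary comparison either require pairs that do not exist or leave the Section 8.1 hypothesis untested.

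Its size differs by reading. Under the literal reading it is mainly a matter of reproducibility near p = 0.05. Under the within-arm reading it is serious, since an ineffective device could readily appear effective. The figures rest on 30 per arm, pilot SDs measured at 4 weeks rather than 8, assumed correlations of 0.3 to 0.7, and assumed differences, shared improvements and dropout. They cover the VAS only; the documents give no SD for BPI-SF.

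**What to change.** In Sections 8.3.1 and 8.3.1.1, replace the paired tests with one prespecified independent-groups analysis of each primary endpoint at 8 weeks, reported as the between-arm mean difference with its 95% CI.

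- **Preferred:** ANCOVA of the 8-week score on arm and baseline score. Relative to change scores, it reduces residual variance by about 17%, 6% and 0% at r = 0.3, 0.5 and 0.7.
- **Minimum:** a two-sample t-test on change, with the Wilcoxon rank-sum test as the non-parametric alternative. The rank-sum test does not estimate the difference in means that Section 3 defines, so it is better kept as supportive.
- **Baseline:** state which pre-treatment VAS counts. The schedule in Section 1.3 marks the 1-week-recall VAS at Screening and Day 1 but not under Baseline, while Section 4.1 lists both baseline and Day 1.
- **Paired tests:** keep them only to describe change within each arm.
- **Optional:** adjust for site, and drop the Shapiro-Wilk switch for the primary analysis so that the data do not choose the test.

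The cost is a rewording of two paragraphs, one sentence on baseline, and the IRB/IEC approval that Section 9.1.1 requires for amendments. No new data or participants are needed. The N and power in Section 8.4 are unchanged, but they refer to responders. For an assumed 12 mm difference, a two-sample t-test with 30 per arm has about 40% to 84% power for r = 0 to 0.7 (SD of change 26.8 to 15.5 mm), and Section 8.4 should say that it does not cover the mean-change analysis.
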